8.2.4 Immunology Study

Principal Investigator: [name] VA Medical Center, Portland

Background and Rationale:

We propose to study the specific cellular immune responses underlying resistance to antiviral therapy in chronic hepatitis C virus infection. For HCV infections, significant differences have been found in the strength and pattern of CD4+ T-cell responses during different stages of disease and in different patient subsets. Missale et al³⁰ⁱ demonstrated that the anti-viral CD4+ T cell response during acute HCV infection was a critical determinant of disease resolution and correlated with a favorable course of infection, i.e., acute self-limited disease. Patients who became HCV-RNA negative and normalized serum aminotransferases had more frequently detectable and significantly stronger CD4+ T cell responses to HCV antigens E2. NS (nonstructural protein) 3. NS4 and NS5 as compared to patients who developed persistent viremia and biochemical evidence of chronic liver injury. Our understanding of the contribution of virus-specific CD8+ cytotoxic T lymphocyte (CTL) responses to viral clearance following antiviral therapy is also incomplete. Nelson and colleagues demonstrated that the presence of detectable HCV-specific CTL activity in liverinfiltrating lymphocytes was associated with a sustained response to subsequent interferon treatment, whereas virus-specific CTLs were not detectable in the liver of interferon nonresponders. ³⁰ Using a TNF- α based ELISPOT assay, Lohr et al³¹ serially analyzed the peripheral blood CTL precursor (CTLp) frequencies specific for HLA A2-restricted T cell epitopes in 11 interferon-q treated patients. Marked increases in CTLp frequencies were observed among therapy responders as compared to non-responders, suggesting that these quantitative multispecific responses could contribute to the reduction of the viral load in treated patients. In fact, the CTL induction observed in non-responders was associated with only transient reductions of the high viral load; therefore, it may be hypothesized that quantitatively insufficient CTL induction could favor resistance to antiviral therapy.

Using highly sensitive assays, we will focus on qualitative, quantitative and kinetic aspects of successful HCV-specific CD4+ and CD8+ T cell responses to create a conceptual paradigm that can be examined by further experiments to facilitate development of vaccines and immunotherapies.

Study Aim:

To study the specific cellular immune responses underlying resistance to antiviral therapy in chronic hepatitis C virus infection, with focus on the qualitative, quantitative and kinetic aspects of successful HCV-specific CD4+ and CD8+ T cell responses in peripheral blood to distinguish responders/non-responders in African Americans and Caucasians.

Study Endpoints:

- (a) Effector frequencies of HCV-specific CD4+ Th1 –producing cells (determined by γ-Interferon ELISPOT). We will use whole proteins for core, E2, NS3, NS4, NS5 and overlapping mer-peptides for regions for which proteins are not available, e.g., p7/NS2, in all patients pre-treatment. We will determine if the magnitude and breadth of CD4+ T cell responses are predictive of response (both early viral kinetics response and long term clinical response).
- (b) Sub-aim, presuming [name] finds cytokine genetic polymorphisms correlate with treatment outcome: The frequency of other cytokine-producing cells (i.e., IL-4, IL-10, TNF-alpha) will be determined using a multiparameter, flow cytometric intracellular cytokine staining assay following PMA (mitogen) stimulation to define the functional relevance of these polymorphisms.
- (c) The kinetics of CD 4+ T cell responses, i.e., the expansion of the number of proteins/peptides that elicit cytokine production (as assessed by Interferon-γ ELISPOT) and the rate at which this occurs after initiation of therapy.
- (d) Frequency of CD8+ T cells specific to NS3 region in 100 patients (see below) will be determined. Using 15-mer-peptides and autologous dendritic cells as antigen presenting cells in the Interferon ELISPOT assay, we will test the hypothesis that HCV-specific CTL specificities and magnitude expand in responders but not in non-responders.

Study Population:

CD4+ studies (N= 400): All 400 patients will be studied to attain adequate power to detect a smaller effect size and because of the lack of data in African Americans (on the one hand, African Americans have less fibrosis and therefore we would expect higher Th1 frequencies; on the other hand, African Americans have lower response rates to treatment and therefore one might predict a lower pre-treatment frequency of Th1 effector cells).

CD8+ studies (N = 100): 100 subjects with genotype 1a 20 will be consented later depending on their response to therapy. These power calculations are based upon unadjusted analyses, and fibrosis and viral load will be controlled for as potential confounding variables using logistic regression modeling.

Method for Analysis/Power Calculations:

CD4 Analyses

Method 1: A two-sample t-test will be utilized to compare the distributions of the number of cells that react between the responders and non-responders. The table below shows the power to detect various effect sizes with α = 0.05, using a two-sided test, and assuming that 33% of the Caucasians will respond to therapy and either 25% or 15% of the African Americans will respond to therapy. Note that effect sizes of 0.4, 0.5, and 0.6 would be considered to be small to medium.²⁹

Table 11							
Racial Group	Power	Proportion Responding To Therapy	Effect Size				
Caucasians	0.76	0.33	0.4				
African Americans	0.86	0.25	0.5				
African Americans	0.86	0.15	0.6				

Method 2: Logistic regression models with responder/non-responder as the outcome variable will be fit to test the detectable increase in the odds of responding for every standard deviation increase from the mean number of cells which show some reaction. These models will be based on both unadjusted and adjusted analyses.

The table below shows the detectable odds ratios from logistic regression analyses, based on 80% power and assuming that 33% of the Caucasians will respond, either 25% or 15% of the African Americans will respond, and a multiple correlation coefficient of 0.4 (i.e., the correlation between the independent variable of interest, the number of cells that react, with all the other independent variables). ³²

Table 12								
Racial Group	Proportion Responding	Odds Ratio (unadjusted)	Odds Ratio (adjusted)					
Caucasians	0.33	1.6	1.7					
African Americans	0.25	1.7	1.8					
African Americans	0.15	1.85	2.0					

Example of Method 2: Given a sample size of 200 Caucasians patients and assuming that one-third will be responders, we will have 80% power to detect an odds ratio of 1.6 for every one standard deviation increase from the mean number of cells that react, using a two-tailed test and $\alpha = 0.05$. This can be interpreted as saying that the odds of being a responder increases by 60% for every one standard deviation increase in the number of cells that react. Adjusting for potential confounders, and assuming a multiple correlation coefficient of 0.4 between the number of cells that react and the other independent variables, we will have 80% power to detect an odds ratio of 1.7.

CD8 Analyses

The number of CD8 cells showing response will be categorized using a clinically meaningful cutpoint. Then the proportion of responders showing greater than the cut-off value of cell responses will be compared to that of the non-responders. This comparison will be done within the racial groups.

Assuming α = 0.05, two-sided test, there will be 80% power to detect a difference if 60% of the responders show greater than the cut-off value of cell responses and 20%, or fewer of the non-responders do. This corresponds to an odds ratio of approximately 6.4. In multivariable analyses, there will be 80% power to detect a difference in proportions between 60% in the responders and 15% or less in the non-responders, using a two-tailed test with alpha equal to 0.05, and assuming a multiple correlation coefficient between the covariate of interest (e.g., responder) and the other independent variables. This corresponds to an odds ratio of about 8.5. These effects are large, however, it is expected that the differences will be substantial and that these are reasonable estimates.

12/08/03

Table 13

Study	Number of Patients	Patient Specifications	Specimen	Minimum Volume per Timepoint
Viral Genetics ([name])	400	Initially, the Viral Genetics study will include at least 96 patients based upon early response pattern and race	Plasma	2 ml (5 ml whole blood)
Viral Kinetics	400		Plasma	2 ml (5 ml whole blood)
Pharmacokinetics	400		Serum	3 ml (7 ml whole blood)
Patient Genetics ([name])	400	NA	Whole blood	15 ml
Interferon Signaling ([name])	All up to and including 4 wks, at least 72 at post- treatment	For 72 (or more), equal number with each early response pattern and race	Whole blood	16 ml
Immunology ([name])	400	All patients will have CD4+ T cell analysis	Whole blood	56 ml at pre for all; 32 ml at 8, 24 wks for all; 48 wks for responders; 56 ml (24 wks post treatment for 300 patients (not assigned to CD8 studies below)
	100 of 400 above	CD8 studies: Genotype 1a; 25 responders, 25 nonresponders in each of the Caucasian and African American racial groups	Whole blood	same schedule as above, but will have 136 ml (instead of 56 ml) drawn at 24 wks post treatment)
Liver Tissue (future studies)	Varies	NA	Liver	Residual from pathology requirements

Ancillary Studies and Viral Kinetics: Number of Patients, Specimen Type

12/08/03

Table 14

Ancillary Studies and Viral Kinetics: Specimen Timepoints and Total Volumes														
	Pre- Treatment		Treatment							Post-Treatment				
	Screen 2	BL Time 0	Day 1	Day 2	Wk 1 (Day 7)	Wk 2 (Day 14)	Wk 4 (Day 28)	Wk 8	Wk 12	Wk 24	Wk 48 Respond -ers only	Wk 24	Additional Follow-Up (4,12,36, 48 Wk) Responders Only	Any Follow-Up Visit***
Viral Genetics ([name])		5ml	5ml	5ml	5ml	5ml	5ml	5ml	5ml	5ml	5ml	5ml	5ml at each time	
Viral Kinetics		5ml	5ml	5ml	5ml	5ml	5ml	5ml	5ml	5ml	5ml	5ml	5ml	
Pharmacokinetics		7ml	7ml	7ml	7ml	7ml	7ml	7ml	7ml	7ml	7ml		7ml §	
Patient Genetics ([name])		15ml												
IFN Signaling ([name])		16ml	16ml	16ml	16ml	16ml	16ml							16ml (at least n=72)
Immunology CD4+ ([name])	56ml							32ml		32ml	32ml	56ml		
Immunology CD8+ ([name])	56ml*							32ml*		32ml*	32ml*	136ml**		
TOTAL Volume	56ml	48ml	33ml	33ml	33ml	33ml	33ml	49ml	17ml	49ml	49ml	66ml (n=300) 146ml (n=100)	10ml at each time + 7ml at follow-up wk 12	16ml (at least n=72)
TOTAL Liver (mm)	Varies											Varies		

Ancillary Studies and Viral Kinetics:	Specimen Timepoints and Total Volumes
---------------------------------------	---------------------------------------

 AL Liver (mm)
 Varies
 Varies

 *
 Will use blood from that taken for the CD4 study (i.e., additional blood will NOT be taken for CD8 at these time points).

 56 ml (= 7 CPT tubes); 32 ml (= 4 CPT tubes)

 **
 136 ml (= 17 CPT tubes) at post treatment week 24

*** Any post treatment visit is suitable, preferably week 24§ Follow-up week 12 for peginterferon alfa-2a only

APPENDIX 1

Proposed Action Criteria for Hepatic Adverse Events (ALT Flares)

1) ALT

Baseline Serum [ALT]	On-Treatment Serum [ALT]	Action
≤100	<200	None
	200 - 300	Repeat test in 1 week. If ALT decreased or stable ($\leq 10\%$ increase), continue at present dose and follow every 1-2 weeks to assure stability. If increased by $> 10\%$, decrease dose by 1 Level and follow with weekly testing until ALT is stable or decreased.
	301 - 500	Repeat test prior to administering dose. If ALT decreased or stable (≤10% increase) , decrease by 1 Level and follow weekly to assure stability. If increased by >10% , hold dose until ALT decreases to <300 then resume study medication at 2 Level decrease and follow every week until stable. If a further 10% increase occurs, stop study medication and complete SAE documentation.
	>500	Hold study medication until ALT decreased to <300 then resume study medication at 2 Level decrease and follow every week. If ALT >300, stop study medication and complete SAE documentation.
101 - 200	≤300	None
	301 - 500	Repeat test prior to administering dose. If ALT decreased or stable ($\leq 10\%$ increase), decrease by 1 Level and follow weekly to assure stability. If increased by $\geq 10\%$, hold dose until ALT decreases to <300 then resume study medication at 2 Level decrease and follow every week until stable. If a further 10% increase occurs, stop study medication and complete SAE documentation.
	>500	Hold study medication until ALT decreased to <300 then resume study medication at 2 Level decrease and follow every week. If ALT >300, stop study medication and complete SAE documentation.
201 - 300	≤400	None
	401 - 500	Repeat test prior to administering dose. If ALT decreased or stable (≤10% increase) , decrease by 1 Level and follow weekly to assure stability. If increased by >10% , hold dose until ALT decreases to <300 then resume study medication at 2 Level decrease and follow every week until stable. If a further 10% increase occurs, stop study medication and complete SAE documentation.
	>500	Hold study medication until ALT decreased to <300 then resume study medication at 2 Level decrease and follow every week. If ALT >300, stop study medication and complete SAE documentation.
301 - 500	≤500	None
	>500	Repeat test prior to administering dose. If ALT decreased or stable ($\leq 10\%$ increase), decrease by 1 Level and follow weekly to assure stability. If increased by >10%, hold dose until ALT decreases to less than baseline then resume study medication at 2 Level decrease and follow every week until stable. If a further 10% increase occurs, stop study medication and complete SAE documentation.
> 500	≤25% Increase	None
	>25% Increase	Repeat test prior to administering dose. If ALT decreased or stable (<10% increase), decrease by 1 Level and follow weekly to assure stability. If increased by >10%, hold dose until ALT decreases to less than baseline then resume study medication at 2 Level decrease and follow every week until stable. If a further 10% increase occurs, stop study medication and complete SAE documentation.

Note: This table is based on an upper limit of normal (ULN) serum ALT of 43 U/L for men and 34 U/L for women. The ULN at the investigator's laboratory should be considered when employing this table.

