4.3 Baseline Visit (Day 0): Once the patient has completed the two screening visits and has been confirmed to be eligible, he/she will return for additional laboratory studies and comprehensive instruction in self-injection techniques by study personnel. These three visits, screening 1, screening 2, and baseline (day 0) will occur within 56 days.

Interim Medical History	
CBC/Differential	
Chemistry	ALT, AST, AlkPO4, total and direct bilirubin, fasting triglycerides, glucose, insulin
Serum Storage	Serum 3ml
Viral Genetics	
Patient Genetics	
Viral Kinetics	HCV RNA quantitative
Pharmacokinetics	Peginterferon alfa-2a levels, 2',5'-OAS serum activity
Interferon Signaling	
Pregnancy Test	Urine
Adherence MATI	
Medication Education	Self-injection techniques (including video), use of MEMS caps, adherence materials
Study Medication Administration	Supervised by research coordinator

Table 6 Baseline (Day 0) visit

4.4 Treatment Period: Pegylated interferon will be administered as a weekly subcutaneous injection and ribavirin will be administered as tablets twice daily. Treatment will be continued for 48 weeks (except in the absence of virological response as defined below). During the treatment period, participants will return for safety and efficacy evaluations at weeks 1, 2, 4, 6 (safety labs only), and 8, and then monthly until treatment is completed.

Efficacy assessment at week 24 will determine if participants are eligible to continue the full 48 weeks of treatment. Participants who have a positive qualitative test result, in duplicate, will be discontinued from study medication at week 24. These participants will then enter the follow-up period and be followed for an additional 24 weeks (post-treatment weeks 4, 12, 24). If they begin other antiviral therapy, they will be discontinued from follow-up.

Interim Medical History	
Symptom-directed Physical Exam	Vital signs and weight at each visit; physical exam every 3 months or as needed
Adverse Event Assessment	
Concurrent Medication Assessment	
CBC/Differential	Each visit (except days 1 and 2)
Chemistry	Each visit except week 1; ALT, AST, AlkPO4, total and direct bilirubin, albumin, uric acid, BUN, creatinine, glucose. Fasting triglycerides, glucose, and insulin at week 24, and week 48 for responders only.
Pregnancy Test	Urine, each visit (except days 1and 2)
TSH	Weeks 12, 24, 36, 48
PT/PTT	Weeks 24 and 48

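### The CD8 hypothesis is about expansion of T-cell responses, but the only CD8 analysis stated compares levels between groups and uses no pre-treatment value

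*Protocol*

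**What the plan says.** Protocol 8.2.4, Study Endpoints (d), sets the CD8 hypothesis: "we will test the hypothesis that HCV-specific CTL specificities and magnitude expand in responders but not in non-responders". It covers two things, breadth (the number of specificities) and magnitude.

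The CD8 Analyses paragraph in the same section gives the test. The count of reacting cells is first dichotomised at a threshold, and the two groups are set against each other: "Then the proportion of responders showing greater than the cut-off value of cell responses will be compared to that of the non-responders". Each race is analysed on its own. A power statement follows: 80% for 60% of responders v 20% of non-responders above the cut-off, two-sided 0.05. The CD8 study-population paragraph names fibrosis and viral load as the confounders to be controlled by logistic regression.

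Table 13 gives the group sizes: "CD8 studies: Genotype 1a; 25 responders, 25 nonresponders in each of the Caucasian and African American racial groups". It also describes the sampling for these 100 patients: "same schedule as above, but will have 136 ml (instead of 56 ml) drawn at 24 wks post treatment". Table 14 assigns blood to CD8 work at Screen 2, weeks 8 and 24, and week 48 for responders. A footnote says that this blood comes out of the CD4 tubes.

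On treatment duration, Section 4.4 says "Participants who have a positive qualitative test result, in duplicate, will be discontinued from study medication at week 24". Under Section 4.5, those who have responded at week 24 are treated for 48 weeks.

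**The concern.** A hypothesis that something expands is tested by comparing each patient with himself or herself before treatment. The stated analysis compares the two groups with each other on a level. The two agree only if the groups started at the same level. Responders and non-responders are formed by outcome and not by randomisation, so nothing in the design secures an equal start.

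The analysis also covers only the number of reacting cells. The breadth half of the hypothesis has no stated test.

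A second difficulty arises if the test uses the large post-treatment draw. There the groups may differ in how long they were treated as well as in whether they responded.

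At stake is what a positive result would mean. As written, it could be reported as therapy-induced CTL expansion in responders when the comparison cannot tell that apart from a higher starting level or, at the late draw, from longer treatment. Dropping the cutpoint and analysing the full count would not cure this.

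**Working it through.** **1. Hypothesis and analysis side by side.**

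| | Endpoint (d) | CD8 Analyses paragraph |
|---|---|---|
| Quantity | change under therapy | level above or below a cutpoint |
| Dimensions | breadth and magnitude | number of reacting cells only |
| Pre-treatment value | needed | not named |
| Time point | before and after start | none named |
| Adjustment | – | fibrosis and viral load (population paragraph) |

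**2. The plan's own power figure.** Inputs from 8.2.4 and Table 13: n = 25 per group within a race, p1 = 0.60, p2 = 0.20, two-sided 0.05. The normal approximation with pooled null variance is

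power = Φ[(|p1 − p2| − 1.96·√(2·p̄(1 − p̄)/n)) / √((p1(1 − p1) + p2(1 − p2))/n)]

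with p̄ = 0.40. The null SE is √(2 × 0.40 × 0.60/25) = 0.1386 and the alternative SE is √((0.24 + 0.16)/25) = 0.1265. So (0.40 − 1.96 × 0.1386)/0.1265 = 1.015, and Φ(1.015) = 84.5%. Fisher's exact test, by enumeration, gives 78.8%. The stated 80% is reproduced. It is power for a difference in level.

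**3. The same test when nobody expands.** Assume that the whole difference was there before treatment and that neither group changes. The rejection rate of the stated test is then its power at the pre-existing proportions. The protocol gives no pre-treatment proportions, so a range is shown; the first row borrows the protocol's target figures.

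| Pre-existing shares above cut-off | Normal approximation | Fisher exact |
|---|---|---|
| 60% v 20% | 84.5% | 78.8% |
| 50% v 20% | 60.9% | 51.0% |
| 40% v 20% | 33.5% | 23.1% |

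The nominal rate is 5%.

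**4. Level test against change test.** Assumptions: normal scale, SD 1, 25 per group. The 60% v 20% split corresponds to a shift of 0.842 + 0.253 = 1.095 SD. The pre/post correlation is set at 0.3, 0.5 or 0.7. By simulation (20,000 runs each):
- Shift present before treatment, no expansion: the level test rejects about 86% of the time, an unadjusted change-score t-test about 5%.
- Shift due wholly to expansion: the change-score test has about 89%, 97% and over 99% power at the three correlations.

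**5. Treatment duration at the dedicated draw.** Week-24 non-responders: 24 weeks of drug, sampled at study week 24 + 24 = 48. Responders: 48 weeks of drug, sampled at study week 48 + 24 = 72. Time off drug is the same, 24 weeks. At on-treatment week 24 both groups have the same planned duration.

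**The case against.** The best defence is that the CD8 paragraph is a short power passage and that the sampling is serial. A pre-treatment CD8 specimen is planned in Table 14, the study aim mentions kinetic aspects, and the paragraph does not say that a single late sample will be tested. Part of the CD8 population text is also visibly garbled. This stands as far as it goes: a reader might infer that no baseline sample exists, or that the test is fixed at the post-treatment draw, and the protocol says neither. It does not rescue the stated analysis. The outcome, comparison, stratum and power are all specified, and together they answer a question about level. That is more than detail deferred to a later plan.

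A reader might also infer that the groups are expected to differ before treatment, because the background reports that CTL activity "was associated with a sustained response to subsequent interferon treatment". That study looked at lymphocytes in the liver, whereas endpoint (d) is measured in blood. The blood study cited beside it was serial and found increases in responders. A baseline gap in blood is therefore possible, not shown.

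It is fair, too, that the rates in step 3 are the test's power under an assumed baseline gap. They show how the test would behave if there were a gap, not how likely the error is.

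Finally, the 48 v 24 week contrast is certain only for week-24 non-responders. The CD8 section does not define responder. If it means SVR, relapsers treated for 48 weeks fall among the non-responders and the imbalance is partial. Patients with discordant or indeterminate week 24 results also follow the responder schedule (Section 3.1). Sampling both groups 24 weeks after stopping is a defensible alignment in itself.

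**Conclusion.** The point holds as a mismatch between hypothesis and stated analysis. Followed as written, the CD8 comparison does not test expansion, and breadth is not analysed at all. The size of the risk depends on an unknown, the pre-treatment difference in blood. With no gap, the level comparison is a reasonable stand-in for magnitude. With a gap of 40% v 20% up to 60% v 20%, a difference would be declared in roughly 23% to 85% of cases although nobody's response expanded. These figures assume 25 v 25 within a race, two-sided 0.05 and no change in either group.

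The duration imbalance is conditional on the post-treatment week 24 sample being the one tested, and may be partial. The documents do not support the stronger readings that the groups are known to start apart, that the false-conclusion rate is 85%, or that exposure always differs two-fold. The matter touches one ancillary endpoint in 100 patients and leaves the SVR comparison untouched. It is worth correcting because the specimens needed are already scheduled.

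**What to change.** Reword the CD8 analysis so that endpoint (d) is tested by the within-patient change from the Screen 2 specimen, in magnitude and in number of reactive peptides, compared between responders and non-responders with adjustment for the pre-treatment value. Include on-treatment week 24 as the time point of equal planned duration. Define responder for this study. The post-treatment week 24 comparison can stay, adjusted for the pre-treatment value, but should not be read alone as evidence of expansion.

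Report the unadjusted change beside the adjusted one. In groups not formed by randomisation the two can disagree. In the no-expansion scenario of step 4, adjustment leaves an expected difference of 1.095 × (1 − ρ), which is 0.77, 0.55 or 0.33 SD at correlations of 0.3, 0.5 and 0.7, while the unadjusted difference in change is zero. A claim of expansion should not rest on the adjusted result alone.

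The cost is a change of text and a fresh power statement, for which the protocol gives no SD or within-patient correlation. No extra draw is needed. There are two limits. The early volumes are smaller and shared with the CD4 work (56 ml at Screen 2 and 32 ml at week 24, against 136 ml), which may restrict the peptides tested in common. And the week 24 comparison still cannot separate expansion from viral clearance, because response at that visit is itself defined by undetectable RNA.
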